In Israel, it is the law that before a patient can be hospitalized involuntarily, he must be evaluated in-person by a senior psychiatrist. The intent of this longstanding policy is to ensure a thorough evaluation before taking the relatively audacious step of hospitalizing a patient involuntarily. However, this policy was created before it was possible to evaluate a patient by video-link. Medical care is increasingly possible via video-link,⁵ but Israel's policy of requiring an in-person evaluation by the senior psychiatrist remains in place. Because the senior psychiatrist is often at home, and not already in the hospital, this policy causes the patient to wait in the ED until the psychiatrist arrives. This additional waiting time can increase the opportunities for the

Protocol Name: Telepsychiatry Emergency; Version: 1.0; Date Nov 5, 2021
patient to decompensate. We will implement evaluation for involuntary admission via video-link, and measure the impact on patient outcomes.

Our study is premised on the idea that reducing friction for patients with psychiatric emergencies, and reducing irritation when they are least equipped to handle it, will lead to reduced opportunities for decompensation and clinical deterioration.² We expect to show that psychiatric ED visits can be shortened, and in many cases, obviated entirely. We expect to show that this approach increases patient safety and promotes quicker resolution of the underlying psychiatric issue.

Many clinical protocols, including those in psychiatry, exist because they have always been done that way, and have never been challenged.⁶ These protocols may have developed by chance, or because it was convenient for physicians, or because of the way hospitals functioned 100 years ago. It is important to reimagine those aspects of medical care that do not have to remain they way they have always been, because they may represent opportunities to improve patient outcomes.⁶

b. Our Group Has Demonstrated that Remote Psychiatric Triage Is Feasible and Valid

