In a prospective observational feasibility study,⁷ our group evaluated 38 patients with psychiatric emergencies who presented to the ED between April and June 2020. Patients were interviewed by two psychiatrists, one face-to-face, and one via video-link, in varying chronological order. Interviewers and a senior psychiatry resident who observed both interviews determined the diagnosis, recommended disposition, and decided whether involuntary admission was warranted for this patient. Patients and psychiatrists completed acceptability post-assessment surveys.

We compared three pairs of assessments for agreement using Cohen's kappa: between the face-to-face interviewer and the remote interviewer, between the observer and the face-to-face interviewer, and between the observer and the remote interviewer. Agreement between raters on recommended disposition and indication for involuntary admission as measured by kappa was "strong" to "almost perfect", ranging from 0.81 to as high as 0.95 (Figure 1). Partial agreement between the raters on diagnosis was "strong", ranging from 0.81 to 0.85. Psychiatrists' and patients' satisfaction rates, and psychiatrists' perceived certainty rates, were comparably high in both face-to-face and telepsychiatry groups. It is notable that while agreement between psychiatrists was not perfect, especially on precise diagnosis, agreement was not materially affected by interviewing the patient remotely. It is also notable that **agreement on recommended disposition and the need for involuntary admission was especially high**. We

Protocol Name: Telepsychiatry Emergency; Version: 1.0; Date Nov 5, 2021
concluded that telepsychiatry is a reliable and acceptable alternative to face-to-face psychiatric assessments in the ED setting.

[figure not shown]

Figure 1: Agreement between raters on recommended disposition, indication for involuntary admission and diagnosis (n=38).

In addition to these measures of agreement, we also measured patients' and providers' satisfaction with the process, as well as providers' level of confidence in their decisions. Patients and providers reported similar levels of satisfaction with remote vs. in-person interviews. Providers reported a similar level of confidence in their clinical decisions with remote vs. in-person interviews.

c. Conceptual Framework and Ethical Analysis

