We will start by comparing the pre- and post-groups on important baseline characteristics. These will include age, sex, ethnic/social group (Haredi, Arab, General Population), socioeconomic status, and underlying condition (schizophrenia, bipolar disorder, other). We will compare these variables between pre- and post-groups using appropriate bivariate tests (t-test, chi-square). If we find a statistically significant imbalance ($p < 0.05$), we will utilize a multivariable analysis in the main analysis to correct for the imbalanced factors. We do not propose to control for all potential covariates because of limited sample size.

In the main analysis, we will compare the dependent variables explained above between the pre- and post-periods. For continuous variables, we will use an unpaired t-test. For categorical variables, we will use a chi-square test. We will perform two-tailed tests, and will consider $p < 0.05$ to be statistically significant. In the event that we have detected an important between-group imbalance, we will use an appropriate regression model (logistic or generalized linear model), controlling for only the factors that have been found to be unbalanced.

Potential Sources of Bias

A sample size of 60 each in the pre- and post-intervention groups will make it unlikely, but not impossible, that random chance will lead to important between-group imbalance on measured factors. We will assess for such imbalance as part of the analysis plan, as noted above. If there are important differences, we will conduct multivariable analyses to control for a limited number of important unbalanced covariates.

Justification of Sample Size and Study Duration

The study duration is dictated by the maximal duration of a study funded by Machon HaLeumi. The sample size is dictated by the approximate number of patients admitted to our center each month. With 60 patients in the pre-intervention period and 60 in the post-intervention period, we will have statistical power to show a large effect size for some variables, and a moderate effect size for others. For example, if we assume that the average time in the ED is currently

3 ± 1 hours, and that the Phase 1 intervention will reduce this time by one hour, with 60 patients in each group, we would have 80% power to detect such a difference.

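### The plan neither checks nor adjusts for which senior psychiatrist handled the patient, so a systematic roster or caseload change between periods would be read as an effect of video

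*Combined protocol and SAP*

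**What the plan says.** Section 4, Patient Population, includes every patient who needs an involuntary admission decision by a senior psychiatrist, and names Kfar Shaul and Ichilov. Under Independent Variables, usual care and video are separated only by calendar period, three months each, with no concurrent control.

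Statistical Analyses sets the main comparison: "For continuous variables, we will use an unpaired t-test. For categorical variables, we will use a chi-square test". The balance check that precedes it covers patient characteristics: "These will include age, sex, ethnic/social group (Haredi, Arab, General Population), socioeconomic status, and underlying condition". Regression is used only if one of the checked factors differs significantly, and then adjusts only for the unbalanced ones. Neither psychiatrist nor site appears among the dependent variables, balance factors or covariates. Potential Sources of Bias deals only with chance imbalance on measured factors.

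Two background statements bear on the role of the psychiatrist. Section 1a explains the wait: "Because the senior psychiatrist is often at home, and not already in the hospital, this policy causes the patient to wait in the ED". Section 1b says of the pilot that "while agreement between psychiatrists was not perfect, especially on precise diagnosis", but also reports kappa of 0.81 to 0.95 for disposition and involuntary admission, which it calls especially high.

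**The concern.** By the protocol's own account, the wait depends on the senior psychiatrist getting to the patient. Time to assessment stops when that psychiatrist begins, and this wait is part of ED length of stay. If psychiatrists differ systematically in how soon they begin, and different people (or the same people in different proportions) cover the two periods, the pre/post difference contains a staffing component. Because all video patients are in one period, the planned tests cannot tell that component from video, and nothing in the plan would reveal it. For 24-hour reversal the route is weaker: it needs systematic differences in admission threshold. For violent incidents it is more indirect still.

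Section 5 hopes that the results may enter Ministry of Health policy, so a staffing difference reported as a benefit of video would matter.

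**Working it through.** **The plan's own figure.** Inputs from Justification of Sample Size: SD 1 h (reading ± as SD), a difference of 1 h, 60 per group, two-sided 0.05.

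- Standard error = 1 × √(2/60) = 0.183 h.
- Power = Φ(1/0.183 − 1.96) = Φ(3.52) = 99.98%.
- The plan says "we would have 80% power to detect such a difference", which does not reproduce. With 60 per group, 80% power corresponds to (1.960 + 0.842) × 0.183 = 0.51 h.

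That is a separate matter and does not decide this point.

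**Model for this point.** Assumed, because the documents are silent: K = 4, 6 or 10 psychiatrists per period, and intraclass correlation ρ = 0.05, 0.10 or 0.20. Total variance is 1 and there is no video effect. Let p₁ₖ and p₂ₖ be psychiatrist k's share of patients in each period, and D = Σ(p₁ₖ − p₂ₖ)².

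- True variance of the difference in means: (1 − ρ)(2/60) + ρD.
- Variance the t-test assumes, with equal caseloads: (2/60)[(1 − ρ) + ρ(1 − 1/K)(60/59)].
- Rejection rate ≈ 2[1 − Φ(1.96 √(assumed/true))].

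With equal caseloads, D = 0 if the same people serve both periods, 1/K if half are replaced, and 2/K if all are.

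**Half replaced, the two extremes.**

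- K = 4, ρ = 0.20: true 0.80/30 + 0.20 × 0.25 = 0.0767; assumed 0.0318; 1.96 × √(0.0318/0.0767) = 1.26; rejection about 21%.
- K = 10, ρ = 0.05: true 0.95/30 + 0.05 × 0.10 = 0.0367; assumed 0.0332; 1.96 × √(0.0332/0.0367) = 1.86; rejection about 6%.

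**Simulation of the planned t-test, equal caseloads, 20,000 runs per cell (rejection, %).**

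| K | ρ | Same people, same shares | Half replaced | All replaced |
|---|---|---|---|---|
| 4 | 0.05 | 4.7 | 9.0 | 13.1 |
| 4 | 0.10 | 3.9 | 13.1 | 21.2 |
| 4 | 0.20 | 3.4 | 20.6 | 32.8 |
| 6 | 0.05 | 4.2 | 7.4 | 10.5 |
| 6 | 0.10 | 4.1 | 10.1 | 15.7 |
| 6 | 0.20 | 3.1 | 14.8 | 24.9 |
| 10 | 0.05 | 4.6 | 6.2 | 7.9 |
| 10 | 0.10 | 4.0 | 7.6 | 10.8 |
| 10 | 0.20 | 2.9 | 10.0 | 16.9 |

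Separate runs of the half-replaced case differ by a point or two at the ends; about 7% to 20% is a fair summary.

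**Chance variation in shares.** If each patient falls to a psychiatrist at random under one unchanged rota with equal shares, the expected D is 2(1 − 1/K)/60. The true variance is then (2/60)[(1 − ρ) + ρ(1 − 1/K)], which is what the t-test assumes on average. Simulation gives 4.6% to 5.8%, so there is no inflation.

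**Rotas redrawn independently for each period** (symmetric Dirichlet shares, parameter 3, which moves about 27% to 30% of the caseload between psychiatrists): about 6% to 13%.

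**Scale.** With the plan's SD of 1 h, the half-replaced roster adds a component with SD √(ρD). This is √(0.20 × 0.25) = 0.22 h (13 minutes) at one extreme and √(0.05 × 0.10) = 0.07 h (4 minutes) at the other. Significance needs a difference of about 1.96 × 0.183 = 0.36 h (21 minutes). A full hour would be 1/√0.0767 = 3.6 standard deviations even at the worse extreme.

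**Psychiatrist as a fixed effect** held rejection at about 4% to 6% in every scenario with overlapping rosters.

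**The case against.** A reader might infer that the documents describe a small pool of psychiatrists known to differ. They do not. No number or roster is given. The travel passage describes a delay of face-to-face care in general, not differences between individuals. The disagreement in the pilot was stressed for precise diagnosis, which is not an outcome here, and imperfect kappa can be case-level noise rather than a systematic psychiatrist effect. Agreement on disposition and involuntary admission was high. All of this stands. It weakens the case for reversal most, but the pilot agreement figures say nothing about timing.

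A reader might also infer that correlation among one psychiatrist's patients invalidates the tests by itself, or that random fluctuation in caseloads does. Neither follows. With the same people and shares the t-test is slightly conservative, and under one unchanged rota chance variation leaves it at about 5%. Replacing one psychiatrist of ten gave 4.2% to 4.7%, although one of four gave 6.7% to 12.3%.

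It is also fair that roster change is one period confounder among several in an uncontrolled before/after study, that the plan limits covariates because the sample is small, that its factor list is open-ended, and that the protocol describes a relatively small feasibility study. This argues against replacing the main test. It does not argue against recording the psychiatrist: unlike most period confounders, this one can be measured with a single field.

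Finally, a psychiatrist effect assumed constant across periods may not hold for waits, because video removes most travel. That limits any adjusted model and is a reason to make it a sensitivity analysis.

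**Conclusion.** The gap is real but conditional. Video and period coincide, the psychiatrist is outside the analysis, and a systematic change in roster or caseload shares would enter the estimated effect unseen. It bears most on time to assessment and ED length of stay, and possibly on 24-hour reversal, for which no size was calculated.

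For 4 to 10 psychiatrists and an intraclass correlation of 0.05 to 0.20, the nominal 5% t-test keeps about 5% under an unchanged rota. It rises to about 6% to 13% with independently redrawn rotas and about 7% to 20% with half the roster replaced. Psychiatrist numbers, correlation and turnover are all assumptions, and no roster change is documented.

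The harm is a false positive for a modest difference rather than lost power. Within these assumptions, half-roster replacement alone would be very unlikely to produce the one-hour reduction the plan uses as its example.

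**What to change.** 1. Record a coded identifier for the deciding senior psychiatrist, and for site, for every patient in both periods. The team already plans to time assessments itself from the pre-intervention period, so the field can be captured there.
2. Tabulate caseload by psychiatrist and period.
3. Keep the planned tests. For time to assessment and ED length of stay, pre-specify a sensitivity analysis with period and psychiatrist as fixed effects, or a random intercept with a small-sample correction. It draws mainly on psychiatrists who worked in both periods. Fixed effects suit so few psychiatrists better: with K = 6 and half the roster changed, an uncorrected random intercept still rejected 6.1% to 7.2%.
4. State that if the rosters do not overlap, psychiatrist and video effects cannot be separated by any model.

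A Mantel-Haenszel analysis by psychiatrist for violence and reversal would add little. With 6 psychiatrists there are about 60/6 = 10 patients per psychiatrist per period, and strata without events contribute nothing.

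The cost is little data collection, some SAP wording, and precision if the roster changes substantially. With half replaced, the fixed-effect comparison rests on about 30 patients per period, so the standard error grows by about √(60/30) = 1.41. The difference detectable with 80% power goes from 0.51 h to about 0.72 h, still below the one hour in the plan's example.

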The arguments in favor of virtual triage in the ED are much stronger. We expect that this change will reduce risk to patients, and risk to others, from violent outbursts. We expect that both phases will reduce patient discomfort, distress, and fear. Lessening decompensation by patients in the ED will allow therapeutic strategies to commence earlier, contributing to earlier recovery and earlier hospital discharge.

It is worth noting that our project is defensible on the basis of benefit to patients alone (otherwise, we would not consider it). There are other likely benefits, which do not enter directly into our calculus. This project is likely to reduce ED crowding. Also, this project will save the attending psychiatrist the need to travel to the hospital for most evaluations. We emphatically repeat that while these are indeed benefits, they are not the basis for us performing the study, nor would they be a sufficient reason for this change in policy.

2. Objectives

- i. We will implement tele-psychiatry evaluations in the ED.
- ii. We will evaluate the impact of this strategy on patient outcomes and healthcare utilization, compared to historical controls.

3. Working Hypotheses

- a. Remote video psychiatric examination is safe and effective, as measured by clinical outcomes, when compared to usual practice. Patients will spend fewer minutes in the ED, compared with historical controls. There will be fewer violent incidents in the ED. There will not be an increase in the frequency of reversal of involuntary hospitalization, which would imply that a patient was needlessly admitted.
- b. Implementation of telepsychiatry will be feasible within the current context, infrastructure, and resources.

4. Comprehensive description of study design and methodology:

Patient Population

We will recruit study participants from the Jerusalem Mental Health Center, located at Kfar Shaul and Ichilov Medical Center. We will obtain a waiver of informed consent, as this will be a change in standard procedure for all patients for the duration of the study.

We will include all patients who require an ED interview and an involuntary admission decision by a senior psychiatrist. We will compare patients from the three months prior to the study (approximately 60, based on usual rates of admissions) with patients from the three months of the study (also 60).

The absence of exclusion criteria will ensure that the study results will be broadly generalizable.

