Independent Variables (The Intervention)

In each study phase, the independent variable will be the study intervention, which will be organized by time. Patients in the pre-intervention period (3 months) will be managed under usual care, and will be the comparison group. Patients in the post-intervention period (3 months) will be managed using the study intervention, and will be the “intervention” group.

Usual care is that patients with psychiatric emergencies are evaluated face-to-face in the ED by a senior psychiatrist for possible involuntary admission. The intervention is that this evaluation will take place via video-link.

Dependent Variables

Dependent Variables

Variable	Type	Data Collection Method
Interobserver Variability	Binary	All video interviews will be recorded. A second senior psychiatrist, blinded to the admission decision, will determine whether admission was warranted based on the recording.
Reversal of Admission	Binary	An involuntary admission which is reversed within 24 hours implies an unnecessary admission. The proportion of admissions reversed within 24 hours will be measured.
Emergency Room Length of Stay	Continuous (minutes)	Measured from the time of arrival in the ED until the patient physically leaves the ED – to go home or to go to the psychiatry ward. Already collected as part of routine practice.
Time from ED arrival to assessment	Continuous (minutes)	We will measure this ourselves, starting with the pre-intervention period. We will measure time until the senior psychiatrist begins his/her face-to-face or virtual assessment.
Violent Incidents in the ED	Binary (any/none)	As recorded by ED staff and adjudicated by blinded review of the chart by a senior psychiatrist.
Patient satisfaction with ED course	Ordinal	We will ask patients to rate their overall satisfaction with their stay in the ED, from 1-5 (very dissatisfied – very satisfied), as they are leaving – starting with the pre-intervention period.
Staff satisfaction with ED flow	Ordinal	We will ask physicians, nurses, and other staff to rate their overall assessment of ED flow, from 1-5, at the end of each month
Duration of hospitalization	Continuous	From the time of entering the ward until the time of leaving the hospital, in hours

Statistical Analyses

We will be comparing the pre-intervention period with the post-intervention period. Above, we have outlined the dependent variables for each phase, and how we will collect them.

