It is possible that for some outcomes, our study will suggest the absence of a harm from the novel strategy, but will not be definitive, and that a larger study may be required in the future. However, this concept (triage via tele-psychiatry) is currently not part of standard practice, and even a relatively small feasibility study, powered to exclude important harms, would be an important step forward.

Collection of Implementation Data

We propose to conduct this study as a hybrid implementation study, Type 1. Hybrid implementation studies aim to shorten the process of translating clinical innovations into practice by simultaneously collecting data about the **effectiveness** of the intervention about the **process** of implementing it.¹⁰ A Type 1 hybrid study primarily emphasizes the collection of effectiveness data, but also includes data collection about the implementation process. If the innovation is found to improve care, as we anticipate it will be, collecting data about the implementation process can help inform future efforts to scale up and spread the innovation to other centers (across Israel, and potentially outside it).¹⁰ To this end, we will interview staff who had a role in implementing the intervention in Phase 1 at the conclusion of Phase 1, when their memories of the implementation process are still fresh. At the conclusion of Phase 2, we will do the same. We will interview staff at various levels of the organization, including senior physicians, junior physicians, nurses, other medical staff, and administrators. Some staff members may be interviewed about both phases. Questions will relate to what went well or badly about the implementation process, what factors facilitated or acted as barriers to implementation, and what advice the respondent would give to someone implementing a similar program elsewhere. We will aim to interview at least 12 individuals total for each phase, since this number is usually sufficient to capture the full range of views on a subject.¹¹ Interviewees will provide consent to be interviewed and to record the interview; those who do not wish to consent will not be included in our study. Interview recordings will be thematically analyzed by our team and will be the subject of a separate report. Participants will not be identified by name in the report.

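### A non-significant two-tailed test cannot support the hypothesis that reversed admissions will not increase, and no calculation backs the statement that the study is powered to exclude harms

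*Combined protocol and SAP*

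**What the plan says.** Section 3, Working Hypotheses, item a, makes a claim of no harm: "There will not be an increase in the frequency of reversal of involuntary hospitalization, which would imply that a patient was needlessly admitted". In section 4, the Dependent Variables table makes reversal a binary outcome with admissions as its denominator: "The proportion of admissions reversed within 24 hours will be measured". The same row treats a reversal within 24 hours as a sign that the admission was unnecessary.

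Statistical Analyses assigns categorical outcomes a chi-square test, replaced by a logistic or generalized linear model if a baseline factor is significantly imbalanced. The decision rule is "We will perform two-tailed tests, and will consider $p < 0.05$ to be statistically significant". No confidence interval, margin or rule for concluding that there was no increase appears in any section.

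Under Justification of Sample Size and Study Duration, the numbers come from patient flow: "The sample size is dictated by the approximate number of patients admitted to our center each month". Power is described only in general terms: "we will have statistical power to show a large effect size for some variables, and a moderate effect size for others". The one worked example is time in the ED. The section ends with a caution that for some outcomes "our study will suggest the absence of a harm from the novel strategy, but will not be definitive", followed by the statement that "even a relatively small feasibility study, powered to exclude important harms, would be an important step forward".

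**The concern.** A two-tailed difference test can support this hypothesis in one way only, through a significant fall in reversals. A significant rise would contradict it. A non-significant result is compatible with no change, a fall or a material rise, and the plan does not say how it will be read. The easy reading, that p > 0.05 means no increase, is not valid.

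The power statement makes that reading more tempting, because it suggests that the study is large enough for a null result on harms to be informative. Nothing in the plan shows this.

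The outcome matters because it stands for needless loss of liberty, and section 5, Significance, links a finding of safety to possible adoption as Ministry of Health policy.

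**Working it through.** **The plan's own figure.** The only power figure is 80% for ED time: SD 1 hour, difference 1 hour, 60 per group. By the normal approximation, power = Φ(1/(1 × √(2/60)) − 1.96) = Φ(5.48 − 1.96) = 99.98%. The stated 80% is not reproduced. That is a separate matter: the example concerns an efficacy outcome and says nothing about harms in either case.

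**Inputs for reversal.** From the plan: 60 per period, chi-square, two-sided 0.05. Assumed, because the plan gives none: baseline reversal rates of 2%, 5% and 10%, margins of 5 and 10 percentage points, and an alternative of 40 admissions per period in case not all 60 assessed patients are admitted.

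**Behaviour of the planned test.** I enumerated all pairs of counts from two independent binomials and applied the uncorrected chi-square.

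| 60 admissions per period | 2% | 5% | 10% |
|---|---|---|---|
| Non-significant, no true change | 98% | 95% | 95% |
| Non-significant, reversals double | 93% | 83% | 67% |
| Significant rise, reversals double | 7% | 17% | 33% |
| Significant fall, reversals halve | 2% | 9% | 17% |

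A non-significant result is therefore the likely outcome whether or not reversals have doubled, except that at 10% a doubling is flagged one time in three. With 40 admissions per period, the chance of flagging a doubling is 4%, 14% and 25%.

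**Worked counts.**
- 3/60 against 9/60, a tripling: χ² = 120 × (3×51 − 9×57)² / (60 × 60 × 12 × 108) = 3.33, p = 0.068. The Wilson limits are 1.7% to 13.7% for 3/60 and 8.1% to 26.1% for 9/60. The Newcombe upper limit is 0.10 + √((0.261 − 0.15)² + (0.05 − 0.017)²) = +0.216. The lower limit is 0.10 − √((0.15 − 0.081)² + (0.137 − 0.05)²) = −0.011. The test is non-significant, yet the data are compatible with a rise of up to 22 points.
- Against 3/60, the smallest study-period count that reaches p < 0.05 is 10/60: χ² = 120 × (3×50 − 10×57)² / (60 × 60 × 13 × 107) = 4.23, p = 0.040.
- 3/60 against 3/60: Newcombe half-width √((0.137 − 0.05)² + (0.05 − 0.017)²) = 0.093, an upper limit of about +9 points. For 2/40 against 2/40 it is 0.121, about +12 points.

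**Could the study exclude a harm?** The table gives the chance that the 95% upper limit falls below the margin when there is no true difference.

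| Margin, n per period, method | 2% | 5% | 10% |
|---|---|---|---|
| 10 points, 60, Newcombe | 83% | 58% | 40% |
| 10 points, 60, Agresti-Caffo | 91% | 67% | 44% |
| 5 points, 60, Newcombe | 25% | 18% | 13% |
| 5 points, 60, Agresti-Caffo | 34% | 18% | 13% |
| 10 points, 40, Newcombe | 52% | 34% | 26% |

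Only the 10-point margin at a 2% baseline with 60 admissions reaches the usual 80%.

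**The case against.** The strongest reply is that the plan already warns the reader. It says results on harm may not be definitive and that a larger study may be needed, and it claims power only for moderate to large effects. The power phrase is one clause in general wording and could describe a type of study rather than this one. The proportions will be measured in both periods, so if the counts are reported anyone can compute an interval later. Every baseline and margin used above is an assumption.

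Much of this is fair, and it lowers the risk of a misreading. But the caution names no outcome and sets no reporting rule, and the sentence directly after it brings the power claim back. That sentence closes the justification of this study's size, so applying it to this study is the natural reading. An interval computed afterwards by a reader does not commit the investigators to basing their conclusion on it. The assumed rates affect only the size of the problem. That p > 0.05 does not show no increase needs no assumption.

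A second reply is that safety is also checked by independent review: "A second senior psychiatrist, blinded to the admission decision, will determine whether admission was warranted based on the recording". This is a partial check. It uses recordings of the video interviews, so it offers no comparison with the earlier face-to-face period.

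**Conclusion.** The concern holds. As written, the plan can support its safety hypothesis on reversals only through a significant fall, which has a chance of 2% to 17% even if reversals truly halve. The likely non-significant result supports no conclusion, because the plan has no interval, margin or reading rule.

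The power statement is unsupported, not disproved. It could hold for a 10-point increase if about 2% of admissions are reversed. By either interval method, it would not hold at 80% for a 10-point increase at baselines of 5% or 10%, or for a 5-point increase at any of the three baselines. These figures rest on the assumed rates and on 60 admissions per period, and they are worse with fewer admissions. The study can go ahead, but this should be corrected before outcomes are compared.

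**What to change.** 1. In Justification of Sample Size and Study Duration, delete the clause that claims power to exclude harms, or replace it with what the design can exclude, giving n and method. For example: with 60 admissions per period and 5% reversed in each, the Newcombe 95% interval for the difference extends to about +9 percentage points (about +12 with 40 admissions).
2. In Statistical Analyses, commit to reporting the risk difference in reversals with a 95% confidence interval, and name the method (Newcombe or score) in advance. State that p > 0.05 will not be taken as evidence of no increase and that any such statement will rest on the upper limit.
3. Preferably, fix a margin before outcomes are compared, and report the result as inconclusive if the upper limit does not exclude it. The choice of margin is the sponsor's.
4. Say whether the 60 per period counts admissions or assessed patients. The population is everyone needing an admission decision, and the ED length-of-stay definition allows for patients who go home, whereas reversal is measured among admissions. This settles the n in item 1.

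The cost is some wording and one extra interval, with no extra patients. The drawback is that the safety statement becomes less favourable and may have to be reported as inconclusive.
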